Since the opening of the University of New Mexico Outpatient Day Surgery Center, breast surgery has been accomplished successfully due to regional anesthesia. Before the development of ultrasound imaging, landmark paravertebral regional anesthesia blocks were placed before surgery to provide post-operative analgesia and enable patients to recover from their surgery in the comfort of their homes. As ultrasound imaging technology was developed and became more mainstream, Paravertebral blocks were then placed using a combination of landmark and live ultrasound imaging while placing the blocks. Ultrasound imaging of the spinal column and the vertebral space is complex. Imaging of bone creates artifact and drop out of the ultrasound image, therefore, creating great difficulty in performing this block under ultrasound-guidance. At the same time, using ultrasound imaging to place these blocks, increases patient safety as the pleura of the lung can be imaged and therefore prevent inadvertent puncture of the lung by the block needle. As technology has further developed, resolution of the paravertebral space is improving and in the hands of experienced ultrasound-guided regional anesthesiologists this block can be placed successfully.

The Paravertebral regional block is considered the gold-standard of anesthetizing the spinal nerves of the thorax and abdomen.ⁱ The block is placed as the spinal nerve root exits the spinal cord and therefore, the somatic and sympathetic parts of the nerve root are anesthetized. Due to the complexity of placing this block, alternative blocks have been sought out that are easier to place and infer better safety for patients.

Recently, the Erector Spinae Plane (ESP) block has been introduced as an alternative to the Paravertebral block.ⁱⁱ It is easier to place in the inexperienced providers hands, easier to teach to new providers and in patients with difficult anatomy sometimes the only safe image that can be obtained for placing a block. The mechanism of action for the Erector Spinae Plane block has not been fully elucidated. Contrast dye studies in cadavers, show that possibly the local anesthetic spreads to the paravertebral space anesthetizing the dorsal ramus of the spinal nerve root where other research demonstrates local spread in the planes of the intercostal muscles reaching lateral cutaneous nerves.ⁱⁱⁱ

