- 4.2. Inclusion criteria: Participants will be drawn from adult female patients having bilateral mastectomy surgery over the age of 18.0 years, who consent to regional anesthesia for their postoperative pain relief. Exclusion criteria: Patients will not be enrolled if they are not yet 18 years old, unable to consent, using anticoagulant medication or have a bleeding disorder, are pregnant (all female patients of childbearing age who present for surgery already receive a urine pregnancy test for non-research reasons), or do not speak English.
- 4.3. Individuals from these protected groups will not be included in this research:
 - Adults unable to consent
 - Individuals who are not yet adults (infants, children, teenagers)
 - Pregnant women
 - Prisoners.
- 4.4. Male patients will be excluded. Bilateral mastectomy surgery is rare in this patient group, and any male patients who do present for such surgery are likely to be experiencing a clinical situation that is distinct from the typical bilateral-mastectomy population; potentially even idiopathic. Enrolled male participants may therefore have an untoward effect on the interpretation of study results, and will be excluded for that reason.
- 4.5. Non-English speakers will be excluded. This is a small unfunded study, and the cost of preparing suitable Spanish-language consent materials would present a substantial burden on the ability of the investigators to proceed. The investigators are not aware of any reason why language preference would affect study results or even correlate with other factors that may affect them, or why results from the contemplated sample could not be reliably extrapolated to patients who speak languages other than English.

5. Number of Subjects

- 5.1. A maximum of 12 participants will be recruited at this site. The planned case series size is 6 participants for whom complete data are available. The excess enrollment capacity is intended to accommodate any participants for whom the planned regional anesthesia techniques cannot be completed adequately. For example, poor ultrasound imaging or particular specifics of patient anatomy may lead to abandonment of an attempt to place regional anesthesia.

PROTOCOL TITLE: Dermatomal spread of Paravertebral and Erector Spinae Plane nerve blocks as compared by thermal imaging

6. Study Timelines

6.1. Describe:

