12.2. Bilateral mastectomy patients will be identified before surgery. Informed consent will be obtained. In the preoperative holding area at OSIS, patient will be positioned in sitting position and a universal time-out will be performed. Patient will have surgical site marking by surgeon and regional site marking by regional anesthesiologist. The PI will randomly draw from a jar the side of the patient that the Paravertebral block will be placed on and the side that the Erector Spinae Plane block will be placed on. Patient will be administered sedation via IV for

PROTOCOL TITLE: Dermatomal spread of Paravertebral and Erector Spinae Plane nerve blocks as compared by thermal imaging

the procedure. Thermal imaging photographs will be obtained using the Flir E95 thermal imaging camera of the posterior, lateral and anterior thorax. The first of three sets of images will be obtained before regional anesthesia (nerve block) placement. Regional anesthesia will be performed as in usual practice for this patient population. The specifics of the block placement will not be modified from our usual practice for purposes of this research project. The patient will receive a Paravertebral block at T4 on one side and an Erector Spinae Plane block at T4 on the contralateral side under ultrasound guidance. Twenty minutes after the blocks are completed, thermal imaging photographs will be obtained of the posterior, lateral and anterior thorax. Ten minutes later another set of thermal imaging photographs will be obtained. The patient will then proceed to surgery. Ultrasound images are all saved under patient's MR per standard of care. Thermographic images will be saved on secure HSC servers under a sequential participant number for later review and analysis.

An example of the thermal image (from reference vii) is provided below:

13.Data Analysis

- 13.1. As this is a case series, formal statistical analysis beyond routine descriptive statistics is not appropriate.
- 13.2. As this is a case series, a power analysis is not appropriate.

14.Provisions to Monitor the Data to Ensure the Safety of Subjects

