The investigators believe that this is a Minimal Risk study, because enrolled patients would be offered regional anesthesia regardless of the existence of this study, there is not a substantial known difference in the success rates of the two regional-anesthesia techniques to be compared, the thermal imaging will not include patient identification, and there will be no deviation from standard procedures for Paravertebral and ESP block placement.

PROTOCOL TITLE: Dermatomal spread of Paravertebral and Erector Spinae Plane nerve blocks as compared by thermal imaging

15. Withdrawal of Subjects

- 15.1. Sometimes due to subject's anatomy a clear ultrasound image cannot be obtained and therefore a regional anesthetic cannot be safely administered. When this occurs, the patient will no longer be a candidate for the study and will be withdrawn. The subject's preblock thermal imaging will be deleted.
- 15.2. All other aspects of care will proceed as if the research did not exist, including accommodation for patients whose blocks cannot be performed.
- 15.3. Any patient who wishes to withdraw will be allowed to do so. The investigators do not anticipate any patient insubordination issues as to research procedures, but any uncooperative patients will be removed from participation and surgery will proceed as normal depending on surgeon preference. Similarly, any participants would be withdrawn if investigators conclude for any reason that their participation presents more risk than benefit.
- 15.4. If a subject withdraws or is withdrawn after thermal imaging is recorded, that subject's thermal images will be deleted.

16. Data Management/Confidentiality

- 16.1. No data will be shared with any external entity, except as required by law.
- 16.2. The research team includes physicians treating prospective and consented participants as patients in the course of their usual job duties, so access to PHI for these patients already exists and is routine.

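### Ultrasound feasibility is judged after the side draw, so where the paravertebral view fails on one side only, whether the patient stays in the study depends on the draw

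*Combined protocol and SAP*

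**What the plan says.** Section 4.2 (inclusion and exclusion criteria) does not require that either block can be imaged.

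Section 12.2 sets out the sequence: consent, positioning and time-out, site marking, the draw, sedation, baseline thermal images, blocks. On the draw: "The PI will randomly draw from a jar the side of the patient that the Paravertebral block will be placed on"; the ESP block goes on the other side. On the images: "The first of three sets of images will be obtained before regional anesthesia (nerve block) placement". No ultrasound check before the draw is described.

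Section 15.1 gives the reason for removal: "Sometimes due to subject's anatomy a clear ultrasound image cannot be obtained and therefore a regional anesthetic cannot be safely administered". The consequence is "When this occurs, the patient will no longer be a candidate for the study and will be withdrawn", and then "The subject's preblock thermal imaging will be deleted". Because baseline images already exist by then, removal comes after the draw in the written order.

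Section 5.1 plans 6 participants with complete data and caps recruitment at 12. The excess covers patients whose blocks cannot be completed; as an example, "poor ultrasound imaging or particular specifics of patient anatomy may lead to abandonment of an attempt to place regional anesthesia".

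Section 2 treats the blocks differently as regards imaging. Bone artefact is described as "creating great difficulty in performing this block under ultrasound-guidance", where the block meant is paravertebral. The ESP view is "in patients with difficult anatomy sometimes the only safe image that can be obtained for placing a block".

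Section 3 calls the study unblinded. Under sections 9.2 and 12.2 the principal investigator makes the draw, places the blocks and takes the images.

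**The concern.** Each patient is her own control, and the random side is what keeps the two blocks on comparable sides. That holds among completers only if staying in the study does not depend on the draw.

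Take a patient whose paravertebral view is inadequate on one side, while the ESP view is adequate on both. If paravertebral is drawn for the poor side, she is withdrawn and can be replaced within the cap of 12. If ESP is drawn for the poor side, both blocks can be placed and she is kept. Every such patient who completes therefore has ESP on her harder side. With 6 completers, each is one sixth of the evidence on the hypothesis of comparable distribution (section 1.1).

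There is a second route. The person who judges whether a view is adequate already knows which block is due on which side.

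The losses would also leave little trace: the images are deleted, and no record of the draw, the failed side or the failed block is specified.

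**Working it through.** **The plan's own figure.** The protocol gives no withdrawal rate and no sample-size formula. The only check available is 6/(1 − 0.5) = 12, so the cap leaves room for 50% losses. It is a ceiling and not a forecast.

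**Inputs**
- Fair draw, 50:50 by side (my reading of the jar draw in section 12.2).
- q = share of patients whose paravertebral view fails on one side only. Assumption; no figure in the documents.
- s = share whose paravertebral view fails on both sides. Assumption; no figure in the documents.
- The ESP view is adequate on both sides. This is a simplification in the direction of section 2, relaxed below.

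**Who is retained**
- No failed view (1 − q − s): all kept, ESP on the harder side half the time.
- One-sided failure (q): half kept, all with ESP on the harder side.
- Two-sided failure (s): none kept, whatever the draw.

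P(ESP on harder side | retained) = [(1 − q − s)/2 + q/2] / [(1 − q − s) + q/2]

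With s = 0 this reduces to 1/(2 − q). The share of completers kept only because of the draw is A = (q/2)/(1 − q/2), and the chance of at least one among 6 is 1 − (1 − A)^6.

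| q (s = 0) | Withdrawn, q/2 | P(ESP on harder side) | Expected of 6 | A | At least one of 6 |
|---|---|---|---|---|---|
| 0 | 0% | 0.500 | 3.0 | 0% | 0% |
| 5% | 2.5% | 1/1.95 = 0.513 | 3.1 | 2.6% | 14% |
| 10% | 5% | 1/1.90 = 0.526 | 3.2 | 5.3% | 28% |
| 20% | 10% | 1/1.80 = 0.556 | 3.3 | 11.1% | 51% |
| 50% | 25% | 1/1.50 = 0.667 | 4.0 | 33.3% | 91% |

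**Two-sided failure.** With s = 25% and q = 0, a quarter of patients are withdrawn and P stays at 0.50. With s = 25% and q = 50%, half are withdrawn and P = (0.125 + 0.25)/(0.25 + 0.25) = 0.75. The number of withdrawals alone therefore does not reveal the imbalance.

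**Letting the ESP view fail too.** A simulation of 2,000,000 patients gave each side a difficulty score, with left-right correlation ρ and a separate failure threshold for each block. All settings are assumptions.

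| Failure rate, paravertebral / ESP | ρ = 0 | ρ = 0.5 | ρ = 0.8 | ρ = 0.95 |
|---|---|---|---|---|
| 10% / 10% | 0.500 | 0.500 | 0.500 | 0.500 |
| 10% / 2% | 0.541 | 0.532 | 0.522 | 0.512 |
| 25% / 5% | 0.605 | 0.577 | 0.552 | 0.526 |

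The shift needs both a higher failure rate for paravertebral and some difference between the sides. At ρ = 1 there is no harder side and no effect.

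**Check before the draw.** If only patients with all views adequate are drawn, P = 0.50 among those drawn (expected 3 of 6), whatever q, s or ρ.

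**The case against.** The strongest reply is that the protocol nowhere says imaging differs between a patient's two sides. Sections 5.1 and 15.1 put failure down to the patient's anatomy and name neither block nor side. If failure is always two-sided, the withdrawals make completers easier cases than the enrolled group but leave the sides balanced. This stands, and it is why the point is conditional.

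Sections 7.2 and 14 also say the success rates are comparable or not known to differ substantially. That tempers the concern but does not remove it: no rates are given, the statements may refer to blocks once placed, and they do not withdraw what section 2 says about imaging.

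Size is a fair objection too. Six fair draws have a standard deviation of √(6 × 0.25) = 1.2 patients and split unevenly with probability 1 − 20/64 = 69%. A shift of 0.1 to 0.3 patients could not be told from chance. The study is a descriptive case series (section 13.1), and section 2 leaves statistical comparison to later randomized studies. However, the shift is systematic and a descriptive comparison carries it as well.

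Finally, a scan may already happen informally at site marking, which precedes the draw. If it governed who was drawn, the effect would disappear. The protocol does not describe one.

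A reader might infer more than the documents support:
- *That completers will in fact tend to have ESP on the harder side.* This needs one-sided failures, which are not documented.
- *That the gap between 6 and 12 shows the plan expects losses of this kind, so all 6 completers could be affected.* Section 5.1 sets a maximum, and poor imaging is only one example of the losses it covers. All 6 affected would require q = 100%.
- *That ESP spread will be understated.* In the scenario at issue the ESP view is adequate, and nothing in the documents links a poor paravertebral view to reduced ESP spread.

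**Conclusion.** The order of events is established by the text: feasibility is an eligibility rule that section 4.2 does not list, and it is applied after the draw with the allocation known. Where the paravertebral view fails on one side only, retention depends on the draw. Given section 2, the resulting imbalance can run only towards ESP on the harder side.

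How far this happens cannot be determined from the documents. For q up to 20% the expected shift is about 0.1 to 0.3 of 6 completers; it reaches a full patient at q = 50% and is zero at q = 0. Bias in the spread comparison needs the further assumption that spread is worse on the harder side. This is a small, conditional weakness, worth correcting because the correction is cheap and makes the result independent of these unknowns.

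**What to change.** - **Section 12.2:** before the jar draw, scan both sides at T4 and record, for each side, whether an adequate view for each technique is obtained.
- **Section 4.2:** draw only patients with both views adequate on both sides. Treat the others as screen failures, who continue usual care as section 15.2 already provides.
- **Section 15.1:** keep it for attempts abandoned after the draw. Log for each the drawn allocation, the side and block that failed, and the reason. The log cannot restore random sides, but it shows whether the mechanism occurred.
- **Reporting:** state that results apply to patients in whom both blocks can be imaged on both sides.

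None of this changes how a block is placed or when an attempt is abandoned.

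The cost is a few minutes of scanning with an operator and equipment already at the bedside, and matching edits to the lists of research-specific procedures in sections 12.1 and 18.1. There will also be more losses before completion, because all one-sided patients are screened out instead of half. At q = 20% (s = 0), 6 completers need on average 6/0.80 = 7.5 patients scanned, against 6/0.90 = 6.7 enrolled now; at q = 50%, 6/0.50 = 12 against 6/0.75 = 8. The amendment should therefore say whether screen failures count towards the maximum of 12. The pool is limited: section 9.2 implies about 2 × 12 = 24 bilateral mastectomies a year at the centre, and one-surgeon referral (section 20.1), the exclusions in section 4.2 and refusals can only reduce it.

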PROTOCOL TITLE: Dermatomal spread of Paravertebral and Erector Spinae Plane nerve blocks as compared by thermal imaging

- E. Provide the external entity(s) contact name, email and phone number with whom the data agreement is going to be executed. List contact information for each external entity(s) that are involved with the project.

Contact Name	External Entity	Email	Phone Number

- F. Who is responsible for transmission of the data?
- G. Who is responsible for receiving the data?
- H. Describe how the data will be securely transmitted/shared . Please note data cannot be transmitted/shared without assistance from UNM HSC Central IT. **Request HSC Central IT Transfer from the ISO office. (cannot transfer via email, cloud storage services such as DropBox OneDrive, and fax)**
- I. For data being transferred/shared with outside locations or entities, describe the following:
1. Where will data be stored and how will it be protected? (i.e. encryption, password protection, access controls, use of REDCap, etc)?
 - o *If REDCap, who manages/owns REDCap (i.e. UNM HSC or other external entity)?*
 - o *If REDCap or other external system is not UNM HSC REDCap managed/owned, please provide the name of owner and the access (login) link?*

Provide IT security point of contact for externally managed/owned REDCap:
 2. What is the method being used for data collection and storage (i.e. electronic, hard copy, etc)?
 3. How long will the data be stored. Must be congruent with sections 16.16-16.18)?
 4. Where will data be stored (UNM HSC requires that research data be stored on the N:\Research-Studies drive managed by HSC Central IT)?
 5. Who will have access to data?
- J. Please list all specific data elements, variables, etc. to be sent out (outgoing) and/or received (incoming).
 What data is incoming?
 What data is outgoing?
- K. What is the classification of the data (de-identified, limited data set, protected health information, other)? See below for definitions:
DE-IDENTIFIED DATA: Identifiers That Must Be Removed to Make Health Information De-Identified:

PROTOCOL TITLE: Dermatomal spread of Paravertebral and Erector Spinae Plane nerve blocks as compared by thermal imaging

(i) The following 18 identifiers must be removed of the individual or of relatives, employers or household members of the individual must be removed: (A) Names; (B) All geographic subdivisions smaller than a State, including street address, city, county, precinct, zip code, and their equivalent geocodes, except for the initial three digits of a zip code if, according to the current publicly available data from the Bureau of the Census: (1) The geographic unit formed by combining all zip codes with the same three initial digits contains more than 20,000 people; and (2) The initial three digits of a zip code for all such geographic units containing 20,000 or fewer people is changed to 000.(C) All elements of dates (except year) for dates directly related to an individual, including birth date, admission date, discharge date, date of death; **and all ages over 89 and all elements of dates (including year) indicative of such age, except that such ages and elements may be aggregated into a single category of age 90 or older;** (D) Telephone numbers; (E) Fax numbers; (F) Electronic mail addresses; (G) Social security numbers; (H) Medical record numbers; (I) Health plan beneficiary numbers; (J) Account numbers; (K) Certificate/license numbers;(L) Vehicle identifiers and serial numbers, including license plate numbers; (M) Device identifiers and serial numbers; (N) Web Universal Resource Locators (URLs); (O) Internet Protocol (IP) address numbers; (P) Biometric identifiers, including finger and voice prints; (Q) Full face photographic images and any comparable images; and (R) Any other unique identifying number, characteristic, or code; and (ii) The covered entity does not have actual knowledge that the information could be used alone or in combination with other information to identify an individual who is a subject of the information.

LIMITED DATA SET: A “limited data set” is a limited set of identifiable patient information as defined in the Privacy Regulations issued under the Health Insurance Portability and Accountability Act (HIPAA). A “limited data set” is information from which “facial” identifiers have been removed. A “limited data set” is information from which “facial” identifiers have been removed. Specifically, as it relates to the individual or his or her relatives, employers or household members, all the following identifiers must be removed in order for health information to be a “limited data set”: names; street addresses (other than town, city, state and zip code); telephone numbers; fax numbers; e-mail addresses; Social Security numbers; medical records numbers; health plan beneficiary numbers; account numbers; certificate license numbers; vehicle identifiers and serial numbers, including license plates; device identifiers and serial numbers; URLs; IP address numbers; biometric identifiers (including finger and voice prints); and full face photos (or comparable images).

The health information that may remain in the information disclosed includes: dates such as admission, discharge, service, DOB, DOD; city, state, five digit or more zip code; and ages in years, months or days or hours.

It is important to note that this information is still protected health information or “PHI” under HIPAA. As a limited data set the information is still subject to the requirements of the federal and state privacy and security regulations.

PROTECTED HEALTH INFORMATION (PHI): PHI is defined as any individually identifiable health information collected or created as a consequence of the provision of health care by a covered entity, in any form, including verbal communications. PHI is

PROTOCOL TITLE: Dermatomal spread of Paravertebral and Erector Spinae Plane nerve blocks as compared by thermal imaging

information that can be linked to a particular person and that is created, used, or disclosed in the course of providing a health care service (i.e., diagnosis or treatment). There are 18 PHI identifiers as listed in the de-identified data definition section.

- L. If the research requires the access, use, or disclosure of any of the 18 individually identifiable protected health information (PHI) identifiers that can be used to identify, contact, or locate a person (e.g., name, medical record number, etc.), are the subjects going to consent to or authorize the disclosure of their individually identifiable health information? Yes No

If yes, please provide details regarding the consent process:

- a. **Or** is HIPAA authorization altered or waived? Yes No

If yes, please provide details:

- M. Does the request to transfer/share data include clinical data that belongs to the UNM Health System? If data originates from the UNM Health System medical records, this question should be answered yes. Yes No
- N. Does the data to be transferred/shared include information about patients seen at an external health system or at a third party medical provider? Yes No
If yes, please provide details:
- O. Is the external entity a “covered entity”? HIPAA-covered entities include health care providers (i.e. hospitals, doctors, academic health centers), health plans, and clearinghouses: Yes No
- P. Is the data that is going to be transferred/shared owned or partially owned by another party? Yes No
If yes, please provide details:
- Q. Does the data have any type of restrictions including regulatory restrictions (i.e. HIPAA, FERPA, etc.)? Yes No
If yes, please provide details:
- R. Is the data publicly available? Yes No
If yes, please provide details:
- S. Does the data include information about substance abuse treatment, sexually transmitted diseases, genetic testing results, HIV/AIDS testing results, and/or mental health ? Yes No
If yes, please provide details:

47. Specimen Transfer/Sharing (Checklist) (required –do not delete even if the answer is “No”)

Provide all requested information if the research involves transferring/sharing of specimens with an external entity (institution, company, etc.).

- A. Will specimens be transferred/shared with an external entity (institution, company, etc.)?

Yes. **If yes, all questions must be answered congruently based on protocol provisions.**

No. **If no, the remainder of this section does not apply.**

PROTOCOL TITLE: Dermatomal spread of Paravertebral and Erector Spinae Plane nerve blocks as compared by thermal imaging

- B. Indicate if the specimens are incoming and/or outgoing:
- C. Provide the name of the entity that specimens will be being transferred/shared with:
